10.0 Study Procedures, Data Management, and Privacy

10.1 Study Procedures

Describe step-by-step how the study will be conducted from beginning to end

Individuals who report interest in the study and report a history of at least one previous TBI, as well as persistent symptoms they believe to be related to that injury, will be enrolled in the study

(see **Figure 1**). Participants will complete a short screen for inclusion and exclusion criteria as dictated for this study. After screening and consenting, participants will be randomly assigned to one of two study arms, the sub-symptomatic adaptable exercise treatment (SAET) treatment group or the stretching control group (SCG) control group, and given a pre-study evaluation to capture baseline functioning. Participants will then be scheduled to begin the study intervention and will receive appointment reminders via phone, text, and/or email. For each participant, randomized to SAET or SCG, additional evaluations will be completed following their last treatment session and at 3 months post-treatment. **Figure 2** details the study procedure timeline.

Participants will be randomized into either the exercise or the stretching condition group in a 1:1 fashion within a block size of 6, which will be utilized until all potential participants are assigned to a group (70 in exercise group and 70 in stretching condition group). Halfway during recruitment, the sample size will be reassessed for balance between the two groups. If needed, adjustment of randomization, for example, to a 2:1 ratio, will be conducted but maintaining the block size of 6. Periodic adjustment may be necessary to obtain the minimum sample size for this project. The study biostatistician will conduct randomization and an assignment schedule will be provided to the project coordinator who will keep such schedule under a password-protected encryption.

Study Evaluations

Participants will undergo the following assessments and evaluations at three study time points: pre-, post-, and 3 months post-treatment.

Cognitive Assessments

Participants will undergo various neuropsychological assessments and complete self-report measures administered via paper and pencil or electronically using an approved data collection platform. Cognitive assessments will take approximately 1 hour to administer at each time point, pre-, post-, and 3 months post-treatment. Specific assessments are described below in Section 10.2.

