12.6 Exclusion Criteria

- History of TBI (any severity) within 1 month of enrollment.
- History of a moderate, severe, or penetrating TBI as defined by DoD/VA guidelines.
- Current substance use disorder.
- History of a neurological disease other than mTBI such as multiple sclerosis, cerebral vascular accident, brain tumor, neurodegenerative disease, or neuro-motor disorder.
- Current, active suicidal or homicidal ideation.
- Impaired decision-making capacity.
- An acute orthopedic injury that limits your capacity to complete study procedures as determined by the study Physical Therapist, PI, and/or medical record review.

- EAS date within 6 months of study enrollment.

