13.0 Recruitment and Consent

13.1 Please describe the recruitment process, including how subjects will be identified and selected for the study

Potential participants will be identified through clinician referrals, responding to IRB-approved study advertisement flyers, through in-person recruitment, and/or word of mouth.

In-person recruitment to occur primarily at:

1. Marine Corps Base Camp Pendleton facilities
2. NHCP and MTF site clinics where SMs, with and without TBI, may receive care (e.g. post-deployment clinics, mental health clinics, pain clinics, PM&R clinics, primary care clinics, neurology clinics)

Additional methods of recruitment include:

1. Posting of recruitment flyers across Camp Pendleton facilities
2. Websites where SMs may find information about research studies will advertise the study with a posted study description, contact information, and a link to the study flyer.

ISC clinicians will be educated about the study by one of the study team members during regularly scheduled clinic meetings, through one-on-one conversations, and through email communications. They will be asked to refer patients who meet basic criteria and express an interest. The clinicians will provide eligible patients with a brief description of the study and ask if they would like to be contacted by a researcher for more information. If the patient is interested, the clinician will inform the appropriate researcher. The researcher will then contact the patient by phone to provide an overview of the study, answer questions, and schedule a screening and consent session.

If a participant self-refers, by contacting the research team in response to a study advertisement or from hearing about the study from someone (e.g., previous participant, friend, coworker, etc.), the research coordinator will take extra care to screen the candidate by verifying information in his/her medical record.

Clinicians and researchers will be responsible for providing potential subjects with an accurate depiction of the study's potential benefits. Subjects will be given an unbiased description of the treatment plan offered by the study. They will be informed that they may or may not benefit directly from the study, and they will not be receiving direct compensation.

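### Section 10.1 gives the assignment schedule to the project coordinator, publishes one fixed block size and names assignment before baseline, with nothing to separate the list holder from enrolment

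*Protocol*

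**What the plan says.** Section 10.1 has the study biostatistician conduct the randomisation and then states that "an assignment schedule will be provided to the project coordinator who will keep such schedule under a password-protected encryption". Participants are randomised "in a 1:1 fashion within a block size of 6, which will be utilized until all potential participants are assigned to a group". Balance is checked halfway through recruitment. If needed, "adjustment of randomization, for example, to a 2:1 ratio, will be conducted but maintaining the block size of 6".

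On the order of steps, Section 10.1 reads: "After screening and consenting, participants will be randomly assigned to one of two study arms", followed, after the arms are named, by "and given a pre-study evaluation to capture baseline functioning". Section 9.5 places the pre-treatment evaluation after screening and consent and does not mention assignment there.

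On who enrols, Sections 13.3 and 13.4 give screening and consent to study researchers. For self-referrals, Section 13.1 says that "the research coordinator will take extra care to screen the candidate by verifying information in his/her medical record". The orthopedic exclusion in Section 12.6 is "as determined by the study Physical Therapist, PI, and/or medical record review".

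Both arms are delivered by a Physical Therapist or Exercise Physiologist (Section 10.1). One arm does aerobic and resistance work and the other stretches. The protocol describes no blinding, no central or sealed release of assignments, and no rule on whether the list holder may also enrol.

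**The concern.** Concealment means that whoever decides on entry cannot know which arm comes next. Encryption protects a file from people without the password, and the coordinator has it. If that person, or anyone who learns the sequence, also influences screening, consent or scheduling, a candidate can be admitted, deferred or declined according to the next arm, without any intent to do so. A single published block size adds a second route that needs no access to the list: staff who track past assignments can work out some of the next ones.

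The arms could then differ at entry. Adjustment can address measured baseline differences but not unmeasured ones, and the intention-to-treat analysis in Section 11.6 would carry any such difference forward. The primary outcome is change in the self-reported Neurobehavioral Symptom Inventory (NSI) and the arms are visible, so concealment up to assignment is one of the few protections this design can still have. If baseline NSI is completed once the arm is assigned, the starting point of the primary outcome is exposed as well.

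**Working it through.** The protocol gives no figure for predictability, so there is none to reproduce. The numbers below are computed from its design.

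**Inputs.** Ratio 1:1, block size 6, contingency 2:1 in blocks of 6 (Section 10.1); 140 participants, 70 per arm (Sections 11.2 and 11.4). Assumption: the observer sees every earlier assignment in order and knows the block size and where blocks begin.

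**1. Assignments known with certainty at 1:1.** A block of 2m = 6 (m = 3) has C(6,3) = 20 equally likely orders. An assignment is certain once one arm has used its three places.
- Fourth place: 2 of 20 orders = 10%.
- Fifth place: 2 × C(4,3) = 8 of 20 = 40%.
- Sixth place: 100%.

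The sum is 0.1 + 0.4 + 1.0 = 1.5 per block. The closed form agrees: 2m/(m+1) = 6/4 = 1.5, and 1.5/6 = 25%. Over the trial, 140 = 23 × 6 + 2. The last two places are never certain, so 23 × 1.5 = 34.5 of 140 (24.6%).

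**2. Correct guesses at 1:1.** The rule is to guess the arm that is behind. Expected correct guesses per block = m + 2^(2m−1)/C(2m,m) − 1/2 = 3 + 32/20 − 0.5 = 4.1 of 6 = 68.3%, against 50% by chance. Over the trial this is 23 × 4.1 + 0.5 + 0.6 = 95.4 of 140, against 70 by chance. The rule needs only the running count of each arm, because every completed block is balanced.

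**3. If the 2:1 contingency is used.** There are C(6,4) = 15 orders. Certain assignments by place: third 1/15, fourth 3/15, fifth 7/15, sixth 15/15. The sum is 26/15 = 1.73 per block, or 28.9%. Enumeration gives 4.47 of 6 guessed correctly (74.4%). The comparator here is 4/6 = 66.7%, from always naming the larger arm.

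**4. Anyone who can open a complete list** knows every assignment on it.

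**5. Randomly mixed block sizes.** Blocks of 4, 6 and 8 (assumed) were simulated in 600 sequences of 140, with an observer who knows the set of sizes and all past assignments.

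| Block sizes | Certain | Best guess correct |
|---|---|---|
| 6 only | 24.6% | 68.2% |
| 4, 6, 8 | 2.4% | 67.9% |

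Mixing sizes removes nearly all certainty and almost none of the guessability. It does nothing about a list that is already held.

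**6. Order of steps.** Section 10.1 names screening and consent, then assignment, then the pre-study evaluation. Section 9.5 names screening and consent, then the pre-treatment evaluation, without placing assignment. Only 10.1 fixes the position of assignment, and it puts it before baseline. This is separate from guessing: on that order the participant's own arm is already settled when baseline NSI and the effort-dependent tests are done.

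**The case against.** Several stronger readings are tempting, and the protocol does not support them.

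- **That the complete sequence is handed over in advance.** The text speaks of an assignment schedule. The whole sequence is the natural reading of something stored under encryption, but it is an inference, and the statement that the holder knows every assignment depends on it.
- **That the list holder is the person who screens.** Section 10.1 names a project coordinator and Section 13.1 a research coordinator. They may be different people, and consent is taken by researchers. On its face, the password keeps the list from the therapist, the investigator and those researchers. What stands is that the protocol never says the roles are separate.
- **That entry is largely discretionary.** The symptom criterion in Section 12.5 is a percentile of published norms, and the mild traumatic brain injury (mTBI) is confirmed by structured interview and records (Section 9.5). The orthopedic exclusion is the clear staff judgement, and record review is one of its stated bases.
- **That 25% and 68% are expected rates.** They are upper bounds. They need full sight of past assignments in order, certainty also needs the block boundaries, and a mid-trial ratio change would alter them.

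It is also fair to credit Section 10.1 with placing screening and consent before assignment, and with having the biostatistician generate the sequence. Nothing suggests that staff would misuse the list. These points narrow the finding. They do not supply the missing barrier between the holder and enrolment, and they do not explain why assignment comes before baseline.

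**Conclusion.** The point holds in this form: followed as written, Section 10.1 does not secure concealment. It gives a schedule to a coordinator whose separation from enrolment is not stated, publishes a single block size and keeps it through any ratio change, describes no single release, and names assignment before baseline.

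At 1:1, up to 25% of assignments could be known with certainty and up to 68% guessed by staff who see all earlier assignments in order. That is plausible at one base with visible arms, but it is an assumption. A reader might infer that enrolling staff know the next arm; the protocol does not establish that. The effect on the treatment estimate cannot be sized from the protocol. Because the remedy costs little, this is best treated as a cheap improvement, and it protects only participants not yet randomised.

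**What to change.** In Section 10.1:

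1. Keep the schedule with the study biostatistician or in a locked randomisation module. Release one assignment at a time, only after eligibility is confirmed, consent is given and the pre-treatment evaluation is complete. Align Section 9.5 with that order.
2. State that no one who screens, consents or assesses participants may hold or view the list.
3. As a secondary step, use randomly varied block sizes (for example 4, 6 and 8) and leave them out of documents held at the site. This cuts certain assignments to about 2% but leaves the best-guess rate near 68%, so it cannot replace steps 1 and 2.

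The cost is one revised paragraph, a matching line in Section 9.5, a short delay per assignment, and reliance on the biostatistician or an automated module being available when participants are ready, up to 140 times. No additional participants are needed.

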Participants will have their oxygen consumption (VO₂) estimated while performing a graded exercise stress test (GXT). Estimated VO₂ is a good indicator of cardiovascular fitness as it measures the heart's ability to supply blood during the demands of aerobic activity. During the GXT, study participants will wear an exercise wearable and/or heart rate monitor to monitor heart activity, as well as a special mask that collects oxygen consumption. The participant will then perform cardio exercise on a machine such as a treadmill or stationary bike for approximately 8 to 12 minutes. During this procedure, trained study staff will closely monitor participants to minimize any risks associated with this exercise. Alternatively, an estimated VO₂ measure may be collected during a graded exercise stress test.

Participants will have their heart rate variability (HRV) measured. HRV is a non-invasive electrocardiographic measurement of the interaction of the sympathetic and vagal tone that is modulated by the ANS (Shaffer & Ginsberg, 2017; Smith, Thayer, Khalsa, & Lane, 2017). HRV describes the amount of variation in instantaneous heart beats as well as the difference between R-R intervals (intervals between QRS complexes that represent ventricular depolarization during normal sinus rhythm). HRV analyzes the tonic sinus rhythm and therefore has been used as an indicator of ANS dysfunction in MTBI (Tan et al., 2009).

Participants will complete a Buffalo Concussion Treadmill Test (BCTT) to determine tolerance to graded exercise. The BCTT protocol involves a modified Balke graded exercise test where participants walk at a steady pace and incline is increased 1% every minute. Symptoms, HR, and RPE are evaluated after each minute stage. The test concludes if participants experience significant symptom exacerbation, defined as an increase of three or more points (based on a 1-10 visual analog scale) above their baseline or reach volitional fatigue, defined as reaching an REP of 19 or 20. Maximum heart rate achieved when test termination criteria have been met will inform whether the participant is requires a subthreshold exercise prescription. Participants unable to complete the BCTT due to injury may have the option to complete a stationary bike equivalent, the Buffalo Concussion Bike Test.

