Participants will be assessed for balance dysfunctions using the Bertec Balance master. This vestibular balance mechanism is designed to measure and treat balance impairments following an mTBI. During this assessment, participants will be secured to the balance platforms via straps with carabiners, which attach to a vest worn by the participant. Once the patient is properly secured, the balance test can begin by selecting the appropriate assessment such as motor control, mobility, and weight shifting. This assessment takes approximately 20 minutes to complete.

Participants will perform isometric strength test to assess the ability to produce force generated through the legs, hips, hands, and arms. The Isometric Midthigh Pull protocol will measure the force being exerted against an immobile object using a dynamometer instead of lifting heavy amounts of weight to determine strength. Participants will be asked to walk up to the racked barbell and resemble a deadlift position that's held at the midthigh. The barbell will be attached to an immobile object via straps and a dynamometer to measure the force being exerted when pulled. The Grip Strength protocol will measure maximal force generated through each hand using a handheld dynamometer. Participants will be asked to remain seated while holding the handheld dynamometer in a 90-degree position and squeeze as hard as possible when given the signal.

Participants will perform a mock Marine Corps Combat Fitness Test (CFT) as administered by study personnel. The CFT is composed of three specific tasks the SM must complete and will take approximately 20 minutes. Each test is scored independently and corrected for gender and age:

- 1) Run: SM completes an 880 yard run. Primary dependent measure is seconds to complete.
- 2) Lift: SM lifts a 30-pound ammunitions can (or equivalent) overhead from shoulder height. Dependent measure is max reps for two minutes.
- 3) Maneuverability: SM completes a simulated maneuver-under-fire event. This is a timed 300-yard shuttle run in which the SM completes a series of tasks: sprints, agility course, high crawl, low crawl, body drag, fireman carry, ammo can carry, push-ups and grenade throw. Dependent measure is seconds to complete.

Command Evaluation

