Work-place evaluation is an important aspect of the study. Each participant will be asked to provide contact information for a direct supervisor who is familiar with on-site work performance. Questions focus on reliability, efficiency of task completion, quality of work performance, independence on the job, as well as military readiness. SMs functioning at their duty station will be assessed by the Checklist of Military Activities of Daily Living (M-ADL). The M-ADL includes 15 items that are detailed in Table 4. In addition to the standard items, 3 items assessing cognitive performance at the workplace will be included. Each item is rated on a Likert scale from "0: Unable to Participate (medical/administrative waiver)" to "7: Complete Independence (timely, safely)". Total score will be used as the primary variable of interest.

If participants are okay with supervisors being contacted the supervisors will fill out a blank survey and return it to the researchers. Participants will not see their supervisor's responses, and supervisors will not see any of the participant's study data. Surveys will be administered online via a secure email link:

https://nhcpr.gov1.qualtrics.com/jfe/form/SV_71npwM0iv2K9XOm

Because work performance evaluation may be a sensitive topic for this population, participants will be asked during the consent process if they give permission for the study team to contact their direct supervisor. If participants do not want their supervisor contacted, then the M-ADL will not be administered. We do not anticipate that the use of the M-ADL will have a direct negative impact on the subject; however, by participating in the M-ADL portion of the study, participants risk that their supervisors will know about the study, and therefore, their participation is no longer anonymous. If participants do not want to accept this risk, they can opt out of this portion of the study.

Study Intervention

Participants will attend two in-clinic sessions per week with a licensed Physical Therapist or Exercise Physiologist and complete three sessions per week independently outside of the clinic. Each session will be 1 hour in duration, 5 days a week for 8 weeks, for a total of 40 hours. Both SAET and SCG interventions will be completed by a trained licensed Physical Therapist or Exercise Physiologist.

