Maximal Aerobic Capacity (VO ₂ max)	Secondary Aim 2	VO ₂ max is a numeric representation of the maximum amount of oxygen that is usable by the body during intense exercise, reflecting the aerobic or cardiovascular fitness level of an individual. The Korr Cardio Coach Plus will be used to capture VO ₂ . The Korr Cardio Coach Plus has been shown to accurately measure submaximal and maximal VO ₂ (Dielic-Conwright, Jensky, Battaglia, McCauley, & Schroeder, 2009).
Balance	Secondary Aim 2	The Bertec Balance Master Smart Balance Manager will be used to asses balance dysfunction pre and post intervention. Patients are secured to the balance platforms via straps with carabiners which attach to a vest being worn by the patient. Once the patient is properly secured, the balance test can begin by selecting the appropriate assessment such as motor control, mobility, weight shifting, etc. The Bertec uses an encircled dome surrounding the balance platform, which projects a moving background giving patients the sensation that they are moving using virtual reality technology (Quintana et al., 2021).
Marine Corps Combat Fitness Test (CFT)	Secondary Aim 3	The CFT is composed of an 880 yard run, max repetitions of an overhead lift of a 30-pound ammunition can, and performance during an under-fire simulated event and completed by all Marines regardless of gender or age. A mock CFT will be proctored by study personnel at baseline, post-treatment, and three months post-treatment.
Military Activities of Daily Living (M-ADL)	Secondary Aim 3	The M-ADL is an evaluation survey which includes 18 items designed to assess performance of SMs by their direct supervisors
Ohio State University Traumatic Brain Injury Identification Method (OSU-TBI ID)		The OSU-TBI ID is a standardized procedure for eliciting a person's lifetime history of TBI via a 3-5 minute structured interview. The validity of the OSU TBI-ID is not based on a perfect accounting of a person's lifetime history of TBI, it is a means to estimate the likelihood that consequences have resulted from one's lifetime exposure

At any point in the study, will you request, use, or access health information in any form, including verbal, hard copy and electronic?

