14.0 Risk and Benefits

14.1 Risk of Harm

Identify all research-related risks of harm to which the subject will be exposed for each research procedure or intervention as a result of participation in this study. Consider the risks of breach of confidentiality, psychological, legal, social, and economic risks as well as physical risks. Do not describe risks from standard care procedures; only describe risks from procedures done for research purposes

The following are some foreseeable risks:

Prescribed Exercise Program: Participants may experience fatigue, muscle soreness, exhaustion, and/or an injury from exercising as a result of engaging in the prescribed physical fitness exercises. We do not anticipate that these risks are more than what this population experiences in their regular fitness routines.

Neurocognitive Assessment: Neurocognitive assessments are designed to be challenging in order to capture peak performance. Subjects may experience frustration and anxiety over performance as they proceed through the assessment.

Physiological Assessments: Physiological assessments are designed to be challenging in order to capture physiological condition. Subjects may experience anxiety, fatigue, nausea, dizziness, skin rash and/or irritation from sensors on wearable devices. Risks of the mock CFT include: muscle strain from overuse of a specific muscle, lower back pain due to poor form, and the chance of dehydration or heat exhaustion on hot days

Warfighter Performance Assessment: work performance evaluation may be a sensitive topic for this population. Participants will be asked during the consent process if they give permission for the study team to contact their direct supervisor. If participants do not want their supervisor contacted, then the M-ADL will not be administered. If participants are okay with supervisors being contacted the supervisors will fill out a blank survey and return it to the researchers. Participants will not see their supervisors responses, and supervisors will not see any of the participant's study data.

Symptom Measures: In order to create a complete picture of symptoms and external factors affecting recovery we will administer measures that ask for personal information such as

emotional state, combat exposure, and childhood experiences. Due to the sensitive nature of the questions, subjects may experience some discomfort while completing these measures.

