14.2 Measures to Minimize Risk of Harm (Precautions, safeguards)

For each research procedure or intervention, describe all measures to minimize and/or eliminate risk of harms to subjects and study personnel

Participants will be instructed to stop exercising for that day if they experience an increase in current symptoms (by 2 points on a 0-10 scale) or onset of two new symptoms of concussion while exercising at home. Also, if participants experience a prolonged or severe increase of concussion-related symptoms during exercise, they should not perform the prescribed exercises and contact their doctor.

Additionally, steps will be taken to ensure participant comfort. Study evaluations will be conducted in comfortable, quiet, and clean testing rooms at the Intrepid Spirit Center. Study personnel will be sensitive to patient discomfort and offer breaks and encouragement when needed and when appropriate.

If participants do not wish for their supervisors to be contacted regarding their job performance through the administration of the M-ADL, participants may opt out of this portion of the research.

If subjects require emergency care for any reason related to the study the NHCP is accessible on base. Adverse events will be reported to the Principal Investigator and IRB within 5 days, as per governing regulations.

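### The cognitive, VO2 and mock CFT outcomes depend on effort, but their testers are neither masked to arm nor separated from the therapists, and encouragement is left to the tester's discretion

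*Protocol*

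**What the plan says.** Section 9.3 states hypotheses on the Global Deficit Score (GDS, sub-aim 1), on Doppler, HRV and VO2 (sub-aim 2), and on the CFT and M-ADL (sub-aim 3). Evaluations take place before treatment, after treatment and 3 months later (10.1).

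On who runs the tests:
- CFT, 10.1: "Participants will perform a mock Marine Corps Combat Fitness Test (CFT) as administered by study personnel". The table in 10.2 repeats this for every time point: "A mock CFT will be proctored by study personnel at baseline, post-treatment, and three months post-treatment".
- Graded exercise test, 10.1: "trained study staff will closely monitor participants to minimize any risks associated with this exercise".
- Cognitive battery: 10.1 names no tester role. On the nature of the tests, 14.1 says: "Neurocognitive assessments are designed to be challenging in order to capture peak performance".

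On who treats, 10.1 says: "Both SAET and SCG interventions will be completed by a trained licensed Physical Therapist or Exercise Physiologist".

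On conduct at study evaluations, 14.2 says: "Study personnel will be sensitive to patient discomfort and offer breaks and encouragement when needed and when appropriate".

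On knowledge of the arm, 10.1 says only that the project coordinator holds the assignment schedule under password-protected encryption. The same section lists random assignment before the pre-study evaluation.

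**The concern.** A timed run, a maximum count of lifts, a graded exercise test and a timed cognitive test all respond to how hard the participant is pushed. If the tester knows the arm and decides who is encouraged and when, effort can differ between arms for reasons unrelated to the treatment. The resulting difference would look like a treatment effect, or would hide one, on GDS, VO2 or the CFT. No analysis can separate the two afterwards, so the safeguard has to sit in the conduct of the trial. It cannot be left to an analysis plan.

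**Working it through.** **Step 1: which outcomes are exposed.**

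| Outcome | Sub-aim | Depends on effort in front of a tester? |
|---|---|---|
| GDS from cognitive tests | 1 | Yes |
| VO2 from graded exercise | 2 | Yes |
| Doppler | 2 | No: automated robotic capture, participant supine |
| HRV | 2 | No: electrocardiographic measurement |
| Mock CFT | 3 | Yes |
| M-ADL | 3 | No: rated by the work supervisor |
| NSI (primary) | – | No: self-report |

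The treadmill test, where participants may "reach volitional fatigue, defined as reaching an REP of 19 or 20", and the grip test, where they must "squeeze as hard as possible when given the signal", depend on effort too. Neither is named in a sub-hypothesis, so they add little here.

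**Step 2: is knowledge of the arm controlled?** Three passages come near it.
- The coordinator's password protection (10.1) covers the schedule. It does not say that testers are kept from the arm.
- Section 10.14 says qualified personnel collect data with standardized protocols. That neither masks the arm nor overrides the more specific sentence in 14.2.
- Section 10.1 says each CFT task is scored independently. That refers to scoring the three tasks separately, not to independent assessors.

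Because assignment is listed before the pre-study evaluation, the arm may be known even at baseline.

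**Step 3: how large could the effect be?** The protocol gives no figure for tester influence, so there is none to reproduce. Inputs from 11.4 and 11.5: 70 per arm, 20% attrition, two-sided alpha 0.05. Evaluable per arm: 70 × 0.8 = 56. Assumption: tester shift b of 0.1 to 0.3 SD, true effect zero.

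Standard error of the difference in SD units: √(2/56) = 0.189. Let k = b/0.189. The two-sided rejection probability (normal approximation) is [1 − Φ(1.960 − k)] + Φ(−1.960 − k).

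| b (SD) | k | In the direction of the shift | Two-sided total |
|---|---|---|---|
| 0 | 0 | 2.5% | 5.0% |
| 0.1 | 0.529 | 7.6% | 8.3% |
| 0.2 | 1.058 | 18.4% | 18.5% |
| 0.3 | 1.587 | 35.5% | 35.5% |

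The two-sample t-test gives 8.2%, 18.2% and 35.0%.

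**Step 4: the CFT is different.** Section 11.6 analyses it as pass or not pass by Poisson regression. As an approximation I used a two-proportion test with 56 per arm, a control pass rate p (assumed, 50% to 90%) and a shifted rate Φ(Φ⁻¹(p) + b).

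| b (SD) | Shifted pass rate, p = 50% / 90% | Prevalence ratio | Significant in the direction of the shift |
|---|---|---|---|
| 0.2 | 57.9% / 93.1% | 1.16 / 1.03 | 13.1% / 8.4% |
| 0.3 | 61.8% / 94.3% | 1.24 / 1.05 | 23.9% / 13.2% |

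The nominal rate in one direction is 2.5%. These figures lie below the continuous ones (18.4% and 35.5%) and depend on the pass rate.

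**The case against.** The protocol is silent rather than wrong: nowhere does it say that testers know the arm or that therapists do the testing. That is correct, and the point claims only that nothing prevents it.

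The encouragement sentence is a comfort measure, placed beside text on quiet testing rooms. It fits the cognitive and other clinic tests most directly and an outdoor run or obstacle course only loosely. That stands. For the CFT the concern rests mainly on the unmasked tester.

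A reader might infer that the bias favours SAET, because 9.6 expects the treatment to speed recovery. The documents do not support a direction. The trigger in 14.2 is discomfort and is neutral between arms. If SAET helps, controls may be the more symptomatic and receive more encouragement.

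A reader might also infer that no positive secondary result could be attributed to SAET. That goes too far, since Doppler, HRV and M-ADL do not depend on the tester in this way. Nor is the bias confined to the post-treatment visits, given the order of assignment and baseline.

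Finally, participants know their own arm, and their expectations may alter effort whoever tests them. This is a separate bias that masked testers would not remove. The affected aims are labelled both secondary and exploratory in 9.3, and the primary NSI is untouched.

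**Conclusion.** The point holds for three outcomes: GDS, graded-exercise VO2 and the mock CFT. For these, the plan as written leaves an avoidable route by which testers can influence the comparison of arms, in either direction. On the assumed shifts of 0.1 to 0.3 SD, the false-positive rate of a continuous outcome would rise from 5% to about 8% to 35%, with a smaller rise for CFT pass/fail. The shifts and pass rates are assumptions for illustration. Nothing in the protocol indicates that a bias of this size, or any bias, will occur. The case for change rests on how easily the route can be closed.

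**What to change.** In 10.1:
- Complete the baseline evaluation before the assignment is disclosed.
- State that the post-treatment and 3-month cognitive, VO2 and CFT tests are run, where the existing roster allows, by study personnel who do not deliver that participant's sessions and are not told the arm.
- Ask participants not to reveal their arm, and log any unmasking.

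In 14.2:
- Replace discretionary encouragement during scored tests with one fixed script, used for every participant at all three time points.
- Leave safety stops and breaks for discomfort unchanged, and record any break taken during a scored test.

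The cost is a wording change, a short script and tighter scheduling, with occasional unmasking by participants. The protocol gives no staff numbers, so it cannot be shown that the roster will always work. If it does not, the script alone still removes the discretion in encouragement.
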